6.2 Sample Size Considerations/Sample Size Justification

6.2.1 Age 18-80

- Sample size for the primary safety endpoint: the overall mean change in HbA1c from baseline to end of 3-month study period, non-inferiority test
 - The overall mean change in HbA1c from baseline to end of 3-month study period from 670G (CEP294 HCL age 18 to 75, N = 101) study was -0.50%. Assuming the mean change in HbA1c from baseline to end of 3-month study period from 780G is the same as 670G, with a standard deviation of 0.7%, SAS power and sample size calculator with one sample T test shows that a total of 80 subjects will provide > 80% power to detect the non-inferiority (with a margin of 0.4%) with a significance level of 0.025 (one-sided).
- Sample size for the primary effectiveness endpoint: the mean % of time in range (TIR 70-180 mg/dL), non-inferiority test
 - The mean % of time in target from 670G (CEP294 HCL age 18 to 75, N = 104) study was 73.7%. Assuming the mean time in target (%) from 780G is the same as 670G, with a standard deviation of 8.8%, SAS power and sample size calculator with one sample T test shows that a total of 80 subjects will provide > 80% power to detect the non-inferiority (with a margin of 7.5%) with a significance level of 0.025 (one-sided).
- Sample size for the secondary effectiveness endpoint: the mean % of time below range (< 54 mg/dL), non-inferiority test
 - The mean % of time below range (< 54 mg/dL) from 670G (CEP294 HCL age 18 to 75, N = 104) study was 0.86%. Assuming the mean time below target (%) from 780G is the same as 670G, with a standard deviation of 0.79%, SAS power and sample size calculator with one sample T

21-APR-2023 Page 9 of 18 Revision 1.0

test shows that a total of 80 subjects will provide > 80% power to detect the non-inferiority (with a margin of 2%) with a significance level of 0.025 (one-sided).

Sample size for the secondary effectiveness endpoint: the mean % of time in range (TIR 70-180 mg/dL), simple superiority test

The mean % of time in target from 670G (CEP294 HCL age 18 to 75, N = 104) study was 73.7%. Assuming the mean time in target (%) from 780G is 76%, with a standard deviation of 7.2%, SAS power and sample size calculator with one sample T test shows that a total of 80 subjects will provide > 80% power to detect the simple superiority with a significance level of 0.025 (one-sided).

6.2.2 Age 7-17

Sample size for the primary safety endpoint: the overall mean change in HbA1c from baseline to end of 3-month study period, non-inferiority test

The overall mean change in HbA1c from baseline to end of 3-month study period from 670G (CEP294 and CEP302 HCL age 7 to 17, N = 125) study was -0.38%. Assuming the mean change in HbA1c from baseline to end of 3-month study period from 780G is the same as 670G, with a standard deviation of 0.7%, SAS power and sample size calculator with one sample T test shows that a total of 80 subjects will provide > 80% power to detect the non-inferiority (with a margin of 0.4%) with a significance level of 0.025 (one-sided).

Sample size for the primary effectiveness endpoint: the mean % of time in range (TIR 70-180 mg/dL), non-inferiority test

The mean % of time in target from 670G (CEP294 and CEP302 HCL age 7 to 17, N = 125) study was 65.3%. Assuming the mean time in target (%) from 780G is the same as 670G, with a standard deviation of 8%, SAS power and sample size calculator with one sample T test shows that a total of 80 subjects will provide > 80% power to detect the non-inferiority (with a margin of 7.5%) with a significance level of 0.025 (one-sided).

Sample size for the secondary effectiveness endpoint: the mean % of time below range (< 54 mg/dL), non-inferiority test

The mean % of time below range (< 54 mg/dL) from 670G (CEP294 and CEP302 HCL age 7 to 17, N = 125) study was 0.71%. Assuming the mean time below target (%) from 780G is the same as 670G, with a standard deviation of 0.60%, SAS power and sample size calculator with

21-APR-2023 Revision 1.0 Page 10 of 18

one sample T test shows that a total of 80 subjects will provide > 80% power to detect the noninferiority (with a margin of 2%) with a significance level of 0.025 (one-sided).

Sample size for the secondary effectiveness endpoint: the mean % of time in range (TIR 70-180 mg/dL), simple superiority test

The mean % of time in target from 670G (CEP294 and CEP302 HCL age 7 to 17, N = 125) study was 65.3%. Assuming the mean time in target (%) from 780G is 67.6%, with a standard deviation of 7%, SAS power and sample size calculator with one sample T test shows that a total of 80 subjects will provide > 80% power to detect the simple superiority with a significance level of 0.025 (one-sided).

6.2.3 Expected Drop-out Rates

Incorporating the expected drop-out rates, a total of up to 250 subjects will be enrolled, in order to have 200 subjects enter the study period.

Statistical Methods 7.

7.1 Study Subjects

7.1.1 General Aspects of Analysis

All data collected from the time of screening until the end of the study will be collected on eCRFs, subject questionnaires, and electronically by uploading the various devices. Data and analysis will be summarized in a Clinical Study Report. Any deviations from original statistical plan and the rationale will be described in the Clinical Study Report.

7.1.2 Disposition of Subjects

The number of subjects enrolled, completed, and early terminated in the study will be presented. The reasons for discontinuing prior to study completion will be summarized.

7.1.3 Clinical Investigation Plan (CIP) Deviations

All protocol deviations will be presented as Listings.

7.1.4 Analysis Sets

[figure not shown]
• Intention to Treat (ITT) Population

The ITT population will include all subjects who start the study period. Primary safety, primary effectiveness, secondary effectiveness and descriptive endpoints will be evaluated for ITT population.

Per Protocol (PP) Population

The PP population will include all subjects who complete the study period, are in SmartGuard feature ≥ 80% of the time and without any major deviations. Primary safety, primary

21-APR-2023 Revision 1.0 Page 11 of 18

effectiveness and secondary effectiveness endpoints will be evaluated for PP population as the sensitivity/supplementary analyses.

Safety Population

The Safety Population will include all enrolled subjects (subjects who signed Informed Consent Form (ICF)). Safety adverse events data summary will be evaluated for safety population.

General Methodology 7.2

Summary statistics for continuous variables will be represented by number of subjects(n), mean, median, standard deviation and categorical variables will be represented by counts and percentages. P-values for hypothesis testing will be evaluated based on one-sided testing using significance level of 0.025. Confidence intervals if needed will be reported as two-sided 95% confidence intervals. For primary safety, primary effectiveness and secondary effectiveness endpoints, normality will be verified for appropriate statistical methodology. Comparisons between the outcomes in study period and the threshold will be performed using one sample T-test for testing the statistical significance of the difference if normality assumption is met or Wilcoxon signed rank test if normality assumption is not met.

The templates for Tables, Listings and Figures (TLFs) will be available in the TLFs document.

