#### 8.2 Subject Enrollment

Subjects will be considered enrolled in the study upon signing the ICF and assent form (if applicable). A subject will be assigned a unique study subject ID via the eCRF, which is a 9-digit code (337XXXXX). The first three digits refer to the CIP number (337), the next three digits refer to the investigational center number, and the last 3 digits refer to the subject number assigned during Visit 1 (e.g., 337002001 is subject 001 from investigational center 002).

The investigator will maintain a log of all subjects enrolled in the clinical study, assigning a subject ID linked to their names, and alternative subject ID.

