## The DMC will perform 3 main functions:

**First:** DMC will track and trend the overall safety of the study. Event rate, defined as number of events per 100 patient years will be reviewed by the DMC with respect to the following:

- Event rate of all SAEs
- Event rate of severe hypoglycemia
- Event rate of severe hyperglycemia
- Event rate of DKA
- Event rate of device related AEs

**Second:** Based on their meetings, DMC will recommend a decision to the sponsor regarding the following:

- Whether or not enrollment should be halted.
- Whether or not the entire study will need to be stopped including for those subjects who have received study devices already.

Note: If it is decided to withdraw subjects from participation in the study or if the study is stopped, subjects will be followed-up in accordance with standard practice by their own providers.

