7.9.6 Safety Data Summarized

Safety data will be summarized based on the following time windows: visit 1 - visit 2, visit 2 - visit 7, visit 7 - the end of study (EOS) or exit, and visit 13 to the end of study (EOS) or exit.

- Serious Adverse Events (SAE)
- Serious Adverse Device Effects (SADE)
- Unanticipated Adverse Device Effects
- Incidence of Severe Hypoglycemia
- Incidence of Severe Hyperglycemia
- Incidence of DKA

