7.10 Safety Evaluation

The safety of the study will be evaluated and summarized per all enrolled subjects, including but not limited to the following:

- Serious Adverse Events (SAE)
- Serious Adverse Device Effects (SADE)
- **Unanticipated Adverse Device Effects**
- Unanticipated Serious Adverse Device Effect
- Incidence of Severe Hypoglycemia
- Incidence of Severe Hyperglycemia
- Incidence of DKA

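### The SAP's only denominator for adverse-event summaries is all consented subjects, so subject-level incidence in the device windows, read as written, can only be biased low

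*SAP*

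**What the plan says.** SAP 7.1.4 (Analysis Sets) defines the safety set by consent: "The Safety Population will include all enrolled subjects (subjects who signed Informed Consent Form (ICF"). It then assigns the adverse-event output to that set: "Safety adverse events data summary will be evaluated for safety population". SAP 7.10 says the same in other words, "The safety of the study will be evaluated and summarized per all enrolled subjects", and lists incidence of severe hypoglycemia, severe hyperglycemia and DKA among the items covered.

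Protocol 8.2 fixes when enrollment happens: "Subjects will be considered enrolled in the study upon signing the ICF and assent form (if applicable"). That is Visit 1. Under Protocol 9.1.1 the study pump and sensor start at Visit 2, once eligibility is confirmed, and SmartGuard with Auto Correction starts at Visit 7.

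SAP 7.9.6 splits the safety output by time: "Safety data will be summarized based on the following time windows: visit 1 - visit 2, visit 2 - visit 7", followed by Visit 7 to end of study or exit, and Visit 13 to end of study or exit. It names no population or denominator for any window. SAP 7.2 says categorical variables are shown as counts and percentages.

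On numbers, SAP 6.2.3 plans that "a total of up to 250 subjects will be enrolled, in order to have 200 subjects enter the study period".

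**The concern.** A subject who fails screening, or who leaves during run-in, cannot have an event on closed-loop therapy in this study. If that subject still counts in the denominator for Visit 7 to end of study, the percentage with an event falls and nothing in the numerator can offset it. The error has one direction, and it favours the device.

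This matters because the formal primary safety endpoint is change in HbA1c. Acute harms appear only in these descriptive summaries, and confirming safety is a stated purpose of the trial. A percentage of all consented subjects is also not comparable with the reference rates in Protocol Table 5, which for all three event types are per 100 patient-years.

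**Working it through.** **Inputs**
- Consented: up to 250 (SAP 6.2.3; Protocol 14.5.3).
- Entering the study period at Visit 7: 200 (same places).
- Starting the device at Visit 2: not given. On the plan it lies between 200 and 250.
- Reaching Visit 13: not given.
- Definition of incidence (subjects, events or person-time): not given in the SAP.

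**The plan's own figure.** SAP 6.2.3 says "Incorporating the expected drop-out rates" but gives no percentage. The two counts imply 1 − 200/250 = 20%, and 200/(1 − 0.20) = 250. The agreement is circular, because the 20% comes from the same two counts.

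**Formula.** With k subjects having an event in a window, E subjects entering it and C consented, the reported percentage is k/C and the percentage among those at risk is k/E. The relative understatement is 1 − (k/C)/(k/E) = 1 − E/C, which does not depend on k.

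**Visit 7 to end of study, E = 200**

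| Consented C | 1 − 200/C |
|---|---|
| 250 (planned maximum) | 20% |
| 240 | 16.7% |
| 230 | 13.0% |
| 220 | 9.1% |
| 210 | 4.8% |

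Example at C = 250: 4 subjects with an event give 4/250 = 1.6% instead of 4/200 = 2.0%. The corrected figure is 250/200 = 1.25 times the reported one.

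**Visit 2 to 7, C = 250, E assumed**

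| Start device E | 1 − E/250 |
|---|---|
| 250 | 0% |
| 240 | 4% |
| 225 | 10% |
| 210 | 16% |
| 200 | 20% |

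**Visit 13 to end of study, C = 250, E assumed**

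| Reach Visit 13 E | 1 − E/250 |
|---|---|
| 200 | 20% |
| 190 | 24% |
| 180 | 28% |
| 160 | 36% |

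The 160 in the last row is the 80 per cohort of the power statements, taken twice. It is not a retention forecast.

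**Person-time.** Subjects who never enter a window add no time to it, so a rate on in-window time has no dilution. For illustration, assume 200 subjects each with 90 days: 200 × 90/365.25 = 49.3 patient-years. Four events then give 100 × 4/49.3 = 8.1 per 100 patient-years, whether 210 or 250 people consented. The SAP does not specify such a rate.

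**The case against.** The strongest reply is that the SAP never says a within-window incidence is divided by all consented subjects. SAP 7.1.4 and 7.10 say whose events are summarised and do not mention windows; SAP 7.9.6 lists windows and does not mention a population. Incidence is undefined, and SAP 7.2 leaves table templates to a separate document, where a column total per window could be set. A reader might infer an explicit rule, and the documents do not support that. What stands is that the consented set is the only one assigned to these summaries. A programmer producing counts and percentages from the SAP would use it. The ITT set, which would fit Visit 7 to end of study, is assigned to the primary, secondary and descriptive endpoints instead.

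A reader might also take 20% as the understatement in every device window. It is the Visit 7 figure at the enrollment ceiling, an upper bound for Visit 2 to 7, and a lower bound for Visit 13 onward at 250 consented and 200 entering.

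Nor do trial conclusions or safety monitoring depend on this. The hypothesis tests use ITT and PP, and SAP 7.9.1 bases success on the primary endpoints. The DMC has its own measure in Protocol 12.2: "Event rate, defined as number of events per 100 patient years will be reviewed by the DMC". Event counts are unchanged, and SAP 7.1.2 reports disposition.

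Finally, the consented set has a proper use. Adverse events are collected from consent (Protocol 11.1) and Visit 1 to 2 is a reporting window, so the definition itself need not be removed.

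**Conclusion.** The point holds as a gap in the safety reporting rules. The SAP gives one denominator for adverse-event summaries, all consented subjects, and reports device windows without naming another. On the natural reading, subject-level incidence of severe hypoglycemia, severe hyperglycemia and DKA in those windows can only be lowered.

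The size for Visit 7 to end of study is up to 20% relative at the planned numbers, and 4.8% to 16.7% if 210 to 240 consent for 200 starters. For Visit 2 to 7 it is 0 to 20%. For Visit 13 onward it is 20% to 36% if 200 to 160 of 250 consented reach that visit. These figures rest on incidence meaning subjects with an event over all consented, and on planned rather than observed counts. In absolute terms the example differs by 0.4 percentage points. The consequence is confined to the descriptive safety tables.

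**What to change.** Keep the all-consented set for adverse-event listings and for Visit 1 to 2. In SAP 7.1.4, 7.9.6 and 7.10, state that for each window from Visit 2 onward the denominator is the subjects who entered that window: device start at Visit 2, then Visit 7, then Visit 13. Report this by age cohort, as the SAP does for its endpoints. State that incidence means subjects with at least one event, and alongside it give events per 100 patient-years of exposure in the window, the unit already used in Protocol 12.2 and Table 5.

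The cost is a few lines of SAP text and one denominator per window, from data already collected. Reported incidences will look slightly less favourable.

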7.9.2 Primary Safety Endpoint

Age 18-80:

The overall mean change in HbA1c, $\Delta\mu_{780G}$, from baseline to end of 3-month study period will be estimated and compared by a non-inferiority test to the threshold of -0.50% with a margin of 0.4%. A significance level of 0.025 (one-sided) will be used. Analysis will be performed on the ITT and PP populations.

The hypothesis of non-inferiority is mathematically expressed as:

$$H_0$$
: $\Delta \mu_{780G} \ge -0.50\% + 0.4\%$
 H_a : $\Delta \mu_{780G} < -0.50\% + 0.4\%$

The null hypothesis will be tested against the alternative hypothesis using one sample t test if normality assumption is met, Wilcoxon signed rank test if normality assumption is rejected. Non inferiority of MiniMed 780G system used in combination with the DS5 CGM for age 18-80 will be concluded if null hypothesis is rejected.

Age 7-17:

The overall mean change in HbA1c, $\Delta\mu_{780G}$, from baseline to end of 3-month study period will be estimated and compared by a non-inferiority test to the threshold of -0.38% with a margin of 0.4%. A significance level of 0.025 (one-sided) will be used. Analysis will be performed on the ITT and PP populations.

The hypothesis of non-inferiority is mathematically expressed as:

$$H_0$$
: $\Delta \mu_{780G} \ge -0.38\% + 0.4\%$

21-APR-2023 Revision 1.0 Page 14 of 18

Ha:
$$\Delta\mu_{780G} < -0.38\% + 0.4\%$$

The null hypothesis will be tested against the alternative hypothesis using one sample t test if normality assumption is met, Wilcoxon signed rank test if normality assumption is rejected. Non inferiority of MiniMed 780G system used in combination with the DS5 CGM for age 7-17 will be concluded if null hypothesis is rejected.

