7.9.3.2 Analysis of Secondary Effectiveness Endpoints

Age 18-80:

Secondary Effectiveness Endpoint: The mean % time, μ_{780G}, in hypoglycemia (< 54 mg/dL [3.0 mmol/L]) will be estimated and compared by a non-inferiority test to the threshold of 0.86% with a margin of 2%. A significance level of 0.025 (one-sided) will be used. Analysis will be performed on the ITT and PP populations. The 2% came from not more than 30 minutes increase in hypoglycemia per day to establish a non-inferiority test.

The hypothesis of non-inferiority is mathematically expressed as:

H₀: $\mu_{780G} \ge 0.86\% + 2\%$

 H_a : $\mu_{780G} < 0.86\% + 2\%$

The null hypothesis will be tested against the alternative hypothesis using one sample t test if normality assumption is met, Wilcoxon signed rank test if normality assumption is rejected. Non inferiority of MiniMed 780G system used in combination with the DS5 CGM for age 18-80 will be concluded if null hypothesis is rejected.

Secondary Effectiveness Endpoint: The mean % of time, μ_{780G}, in range (TIR 70-180 mg/dL [3.9 -10.0 mmol/L]) will be estimated and compared by a simple superiority test with a significance level of 0.025 (one-sided). Analysis will be performed on the ITT and PP populations.

The hypothesis of superiority is mathematically expressed as:

 H_0 : μ_{780G} ≤ 73.7%

[figure not shown]
 H_a : $\mu_{780G} > 73.7\%$

The null hypothesis will be tested against the alternative hypothesis using one sample t test if normality assumption is met, Wilcoxon signed rank test if normality assumption is rejected. Superiority of MiniMed 780G system used in combination with the DS5 CGM for age 18-80 will be concluded if null hypothesis is rejected.

Age 7-17:

Secondary Effectiveness Endpoint: The mean % time, μ_{780G} , in hypoglycemia (< 54 mg/dL [3.0 mmol/L]) will be estimated and compared by a non-inferiority test to the threshold of 0.71%

21-APR-2023 Revision 1.0

Page 16 of 18

with a margin of 2%. A significance level of 0.025 (one-sided) will be used. The 2% came from not more than 30 minutes increase in hypoglycemia per day to establish a non-inferiority test. Analysis will be performed on the ITT and PP populations.

The hypothesis of non-inferiority is mathematically expressed as:

 H_0 : $\mu_{780G} \ge 0.71\% + 2\%$

 H_a : $\mu_{780G} < 0.71\% + 2\%$

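### The confirmatory hypotheses concern means, but a failed normality check switches the test to Wilcoxon signed-rank, which tests a different parameter, so the one-sided 0.025 level is not assured

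*SAP*

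**What the plan says.** SAP 7.9.2 (HbA1c change), 7.9.3.1 (time in range, non-inferiority) and 7.9.3.2 (time below 54 mg/dL, and time-in-range superiority) each write the null and alternative for a population mean. The comparator is a historical mean, with a margin where non-inferiority is tested. This holds in both age cohorts.

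SAP 7.2 General Methodology says that for all these endpoints "normality will be verified for appropriate statistical methodology". It then assigns the one-sample t-test "if normality assumption is met or Wilcoxon signed rank test if normality assumption is not met". Each endpoint section repeats the rule ("Wilcoxon signed rank test if normality assumption is rejected") and attaches one conclusion to whichever test is run. For adults, non-inferiority of the system "used in combination with the DS5 CGM for age 18-80 will be concluded if null hypothesis is rejected". No normality test, significance level or graphical criterion is named, and the SAP does not say that the target parameter changes with the test.

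Two other places rest on the mean. The margin for time below 54 mg/dL is justified in minutes per day: "The 2% came from not more than 30 minutes increase in hypoglycemia per day to establish a non-inferiority test". The sample-size sections use only the t-test: "SAS power and sample size calculator with one sample T test shows that a total of 80 subjects". SAP 6.2.1 and 6.2.2 repeat that basis for all eight hypotheses.

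**The concern.** The signed-rank test is a test of the mean only when the distribution is symmetric about it. Otherwise it tests the pseudo-median, the median of the averages of pairs of observations. Under right skew the pseudo-median lies below the mean, so a test for a low value rejects too often when the mean is exactly at the bound. Under left skew the same holds for a test for a high value.

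The parameter actually tested therefore depends on an unspecified preliminary test, and it may differ between endpoints and between cohorts. The level of 0.025 that SAP 7.5 relies on in its fixed sequence is then not assured for the hypotheses as written. Time below 54 mg/dL is where this is easiest to foresee. It also stands before time-in-range superiority in that sequence (SAP 7.5.1 and 7.5.2), so its error control bears on the multiplicity claim. The same rule governs HbA1c change, which helps decide cohort success under SAP 7.9.1.

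**Working it through.** **1. The plan's own power figures.** Inputs from SAP 6.2.1 and 6.2.2: n = 80 and one-sided 0.025. The noncentrality is δ√n/SD.

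- HbA1c, both cohorts: 0.4 × √80 / 0.7 = 5.11, power 99.9%.
- Time-in-range superiority, adults: (76 − 73.7) × √80 / 7.2 = 2.86, power 80.6%.
- Time-in-range superiority, children: (67.6 − 65.3) × √80 / 7 = 2.94, power 82.7%.
- Time-in-range non-inferiority and time below 54 mg/dL: about 100%.

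The stated power above 80% therefore reproduces, using the t-test.

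**2. Time below 54 mg/dL cannot be close to normal at the planning values.** It is bounded below by zero. With the planning mean and SD, a normal curve would put Φ(−0.86/0.79) = 14% of adults and Φ(−0.71/0.60) = 12% of children below zero.

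**3. Error at the bound for time below 54 mg/dL.** The bounds are 0.86 + 2 = 2.86% and 0.71 + 2 = 2.71%. The SDs are the SAP's, 0.79% and 0.60%. The following are assumptions, because the documents do not give them: a gamma shape with mean at the bound (skewness 2 × SD/mean = 0.55 in adults, 0.44 in children), Shapiro-Wilk at 5% as the check, and n = 100 if the 200 subjects entering the study period split equally. There were 40,000 simulated trials per case, with a Monte Carlo standard error of about 0.1 point.

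| Cohort, n | t-test | Wilcoxon always | Switch rate | SAP rule |
|---|---|---|---|---|
| Adults, 80 | 3.0% | 6.0% | 40% | 5.1% |
| Adults, 100 | 3.0% | 6.8% | 49% | 6.0% |
| Children, 80 | 2.8% | 5.0% | 28% | 4.2% |
| Children, 100 | 2.8% | 5.4% | 34% | 4.5% |

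A hand check explains the Wilcoxon column. The pseudo-median at the bound is 2.824 in adults, 0.036 below the mean. The standard error at n = 80 is 0.79/√80 = 0.0883, so the shift is 0.036/0.0883 = 0.41 standard errors, and Φ(−1.96 + 0.41) is about 6.0%. In children the pseudo-median is 2.688, the shift is 0.022/(0.60/√80) = 0.33, and Φ(−1.96 + 0.33) is about 5.1%. The shift does not shrink as n grows, so the excess rises with n.

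Range under other assumed shapes, n = 80 to 100: a lognormal with the SAP's SD gives about 6.5–10% under the SAP rule, against 3.0–3.5% for the t-test. A gamma whose SD grows in proportion to the mean gives 25–33% against 4.1–4.6%. The last is illustration only, since the documents do not give the spread at the bound.

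**4. The other endpoints under the SAP rule, n = 80 / n = 100.**

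| Endpoint (assumed shape) | Adults | Children |
|---|---|---|
| Time in range, non-inferiority (beta) | 3.4% / 3.3% | 2.7% / 2.6% |
| Time in range, superiority (beta) | 3.5% / 3.8% | 3.0% / 2.9% |

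For HbA1c change with SD 0.7% and an assumed skewness:

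| Skewness | −1 | −0.5 | 0 | +0.5 | +1 |
|---|---|---|---|---|---|
| n = 80 | 0.6% | 1.7% | 2.6% | 4.6% | 11% |
| n = 100 | 0.3% | 1.5% | 2.6% | 5.3% | 13% |

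The t-test stays within about 1.8–3.6% across these HbA1c cases.

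**5. At the planning means.** Time below 54 mg/dL passed in 100% of 10,000 simulated trials in both cohorts under the t-test, under Wilcoxon and under the SAP rule. The switch to Wilcoxon occurred in all of them.

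**The case against.** The strongest reply is that the excess error arises where the trial is unlikely to be. The adult planning mean for time below 54 mg/dL lies 2/(0.79/√80), or about 22 standard errors, from the bound. The tests disagree only within a few tenths of a point of that bound. The endpoint is secondary and outside the pass/fail rule. Near-certain switching occurs at the planning mean, where the choice of test is immaterial; at the bound, with the planning SD, the assumed gamma is mild and the switch happens in only 28–49% of trials. Means are reported in any case, so a mean close to the bound would be seen. For the endpoints that decide success, time-in-range non-inferiority is close to nominal, and the HbA1c figures rest on a skewness that nobody has stated. Nor does the t-test hold exactly 2.5% under skew.

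All of this stands, and it limits the weight of the point. It does not remove the mismatch: the formal decision rule can reject a true hypothesis about a mean at a rate other than the stated level, and reporting the mean does not change that decision. Prespecifying the rule does not help either, because the step that selects the test is left undefined.

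**Conclusion.** The concern holds: the plan states hypotheses about means and, in some datasets, would decide them with a test of another parameter. This follows from the text and needs no assumption. The size does need assumptions. For time below 54 mg/dL at the bound, with a gamma shape, the SAP's SDs and a 5% Shapiro-Wilk check, the one-sided error is about 4–6% against about 3% for the t-test. The switch itself adds about 2.2–2.9 points in adults and 1.4–1.7 in children. Primary time-in-range non-inferiority is at most 3.4% under an assumed beta shape. For HbA1c, direction and size are unknown. The documents do not show that cohort success is in danger. This should be fixed, at low to moderate practical weight.

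**What to change.** Delete the normality-dependent choice of test in SAP 7.2 and in each endpoint section of 7.9.2 and 7.9.3. Name the one-sample t-test, reported with its confidence limit for the mean, as the primary analysis for all confirmatory endpoints. Keep the Wilcoxon signed-rank test as a sensitivity analysis, labelled as addressing the pseudo-median. A bootstrap-t upper limit for the mean of time below 54 mg/dL could be added as a further sensitivity analysis.

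This brings the hypotheses, test, interval and sample-size basis into line. It needs SAP wording and a few lines of code, with no change to sample size. The cost is a little power for time-in-range superiority. In simulation with an assumed beta shape, adults go from 81.9% to 79.8% at n = 80 and from 89.6% to 87.7% at n = 100. Children go from 82.9% to 82.3% and from 90.4% to 89.9%. Power for the other endpoints stays above 99%. The t-test will still run slightly above 2.5% for right-skewed time below 54 mg/dL, about 3% under the gamma assumption, and the SAP may say so.
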